1 INTRODUCTION

1.1 BACKGROUND

In 2006, the standard duration of adjuvant endocrine therapy for breast cancer (either SERMs or AIs) is five years. Patients who receive extended adjuvant letrozole for five years following approximately five years of tamoxifen obtain further benefit compared with the five years of tamoxifen alone. Similarly, benefit has been demonstrated for switching from tamoxifen to an AI after 2 to 3 years of tamoxifen to complete five years of endocrine therapy, as well as initiating therapy with AI following surgery and administering the AI for five years.

[figure not shown]
Questions remain about the optimal duration and best schedule of AIs in the extended adjuvant setting. This trial tests the hypothesis that introducing 3-month treatment-free intervals during the course of five years of extended adjuvant letrozole will improve disease-free survival. This hypothesis is based on the theoretical principle that letrozole withdrawal for 3 months will permit some estrogenic stimulation which makes residual resistant disease susceptible to letrozole reintroduction.

1.2 TRIAL DESIGN

SOLE (IBCSG 35-07 / BIG 1-07) OVERVIEW

Title:	Study Of Letrozole Extension (SOLE): A phase III trial evaluating the role of continuous letrozole versus intermittent letrozole following 4 to 6 years of prior adjuvant endocrine therapy for postmenopausal women with hormone receptor positive, node-positive early stage breast cancer.
Patient Population:	Postmenopausal women who are disease-free following 4-6 years of prior adjuvant endocrine therapy with selective estrogen receptor modulator(s) (SERM) and/or aromatase inhibitor(s) (AI) for endocrine-responsive, node-positive early breast cancer.
Entry:	Patients must have stopped prior endocrine SERM/AI therapy, and must be randomized within 12 months (1 year) of the last dose of prior endocrine SERM/AI therapy.
Activation Date:	8 November 2007 (First patient randomized on 5 December 2007)
Target Accrual:	4800 patients
Closure Date:	12 July 2012 (Last patient randomized on 8 October 2012)
Final Accrual:	4884 patients

Trial Schema:

The SOLE trial is a multinational phase III randomized clinical trial designed to compare continuous letrozole for 5 years with intermittent letrozole over a 5-year period among postmenopausal women who are disease-free following 4 to 6 years of prior adjuvant endocrine therapy with SERM(s) and/or AI(s) for endocrine-responsive node-positive operable breast cancer. The hypothesis is that introducing 3 month treatment-free intervals during the course of 5 years of extended letrozole will improve disease-free survival.

The randomization was stratified according to participating center and prior SERM/AI endocrine therapy (SERM(s) alone, AI(s) alone, both SERM(s) and AI(s)). Patients were randomized 1:1 to one of two extended adjuvant endocrine therapy groups:

A: Continuous letrozole 2.5 mg daily for 5 years

B: Intermittent letrozole 2.5 mg daily for the first 9 months of years 1 through 4, with treatment-free intervals for the last 3 months of years 1 through 4, followed by 12 months of letrozole 2.5 mg daily in year 5

Patients should start trial treatment as soon as possible after randomization. Trial treatment should begin no later than 6 weeks from the date of randomization. All patients will be followed every 6 months for years 1 to 5, and yearly thereafter for assessment of disease status and for survival data collection.

1.3 SAMPLE SIZE CONSIDERATIONS

The sample size was determined to provide 80% power to detect a 20% reduction in the risk of an event defining DFS associated with intermittent letrozole compared with continuous letrozole (hazard ratio = 0.80; 25% increase in 4-year DFS from 90% to 91.917%) using a two-sided 0.05 level test of significance.

To detect the treatment difference 647 DFS events are required, assuming 4800 patients are accrued (1600 patients per year for 3 years), 5% non-assessability at 4 years, and approximately 5 years of additional follow-up. One year of start-up time, as Participating Centers obtain Ethics Committee approval and complete regulatory processes, is anticipated.

1.4 INTERIM MONITORING PLAN (FROM PROTOCOL)

A group sequential design with two interim analyses and one final analysis is used. The target number of events for the final analysis is 647, and interim analyses are planned after 40% and 70% information (259 and 453 events observed respectively). At each interim analysis and at the final analysis, testing will be performed using O'Brien-Fleming boundaries.

1.5 DATA AND SAFETY MONITORING COMMITTEE REVIEWS

The Data and Safety Monitoring Committee (DSMC) reviews the safety information, including adverse events, second (non-breast) malignancies, and deaths without prior cancer event, every six months and has recommended the trial continue as planned. The first interim efficacy analysis was performed for spring 2014 DSMC report when 324 DFS events (50% information) were observed. At that time the O'Brien-Fleming boundary was not crossed and there was not enough evidence to support early stopping of the trial due to efficacy. The DSMC recommended that SOLE treatment administration and follow-up continue as planned. The same results held for the second interim efficacy analysis which was performed for spring 2015 DSMC report when 454 DFS events (70% information) were observed.

2 EFFICACY ANALYSIS PLANS

2.1 OBJECTIVES

The primary objective is to compare continuous letrozole for five years with intermittent letrozole over a five year period for postmenopausal women who are disease-free following 4-6 years of prior adjuvant endocrine therapy with SERM(s) and/or AI(s) for endocrine-responsive, node-positive, operable breast cancer.

2.2 ANALYSIS POPULATIONS

The primary analysis will use an intention-to-treat (ITT) approach. The ITT population will include all randomized patients, regardless of eligibility status; the possible exceptions are patients who immediately withdrew consent prior to treatment initiation and declined all participation, patients determined (e.g., via audit) to be without documented informed consent, and/or patients at a participating center determined not to be compliant with protocol procedures. Any exclusion from the ITT population will be determined prior to the analysis and will be summarized in listing and CONSORT in the trial report.

2.3 ENDPOINT DEFINITIONS

2.3.1 Primary Endpoint

- Disease-free survival (DFS) is defined as the duration of time from randomization to the first indication of the following events: invasive recurrence at local (including recurrence restricted to the breast after breast conserving treatment), regional or distant sites; a new invasive cancer in the contralateral breast; any secondary (non-breast) malignancy; or a death without prior cancer event. Appearance of DCIS or LCIS either in the ipsilateral or in the contralateral breast will not be considered as an event for DFS. In the absence of an event, DFS is censored at the date of last follow-up.

2.3.2 Secondary Endpoints

- Overall survival (OS) is defined as the duration of time from randomization to death from any cause, or is censored at the date last known alive. (Note, for patients who withdrew consent or were lost to follow-up but follow-up for survival was possible through hospital or registry records, OS is censored at the date last known alive rather than date of last follow-up/withdrawn consent).
- Distant disease-free survival (DDFS) was a secondary endpoint in protocol. It will be replaced by a more modern definition -- distant recurrence-free interval (DRFI) defined as the duration of time from randomization to the first indication of invasive breast recurrence at a distant site. In the absence of an event, DRFI is censored at the date of last follow-up or date of death without distant recurrence.
- Breast cancer-free interval (BCFI) is defined as the duration of time from randomization to the first indication of the following events: invasive breast recurrence at local, regional or distant sites; a new invasive cancer in the contralateral breast. In the absence of an event, BCFI is censored at the date of last follow-up or date of death without prior breast cancer event. (Second non-breast malignancies are ignored)
- Site of First Failure: Hierarchy of failures from least to worst, following standard IBCSG definition:
 - o Local
 - o Contralateral Breast
 - o Regional ± above
 - o Soft Tissues/Distant Nodes ± above
 - o Bone ± above
 - o Viscera (including 'other') ± aboveas well as incidence of 2nd (non-breast) malignancy, death without prior cancer event, and adverse events.

For “site of first failure,” if there are 2 or more failure sites within 2 months of each other, then the “worst” site is considered as the site of first failure. For example if there is a regional recurrence and a bone recurrence within 2 months of each other, then the bone would be

considered the “worst” site of failure and considered as “site of first failure.” If second malignancy is coincident with breast cancer recurrence then site of first failure is considered as the breast cancer recurrence.

Per IBCSG standard, the date of DFS event is the date a proven recurrence was first suspected. In rare cases that the date suspected is prior to randomization, date of randomization is considered as date of event.

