#### **Trial end points**

Primary end point: Disease-free survival (DFS): time from randomization to local (including invasive recurrence restricted to the breast after breast conserving treatment), regional or distant relapse, contralateral breast cancer, appearance of a second (non-breast) malignancy, or death from any cause, whichever occurs first.

Secondary end points: overall survival (OS), distant disease-free survival (DDFS), breast cancer free interval (BCFI), sites of first failure, second (non-breast) malignancies, deaths without prior cancer events, and adverse events.

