### **2.2. Secondary endpoints**

2.2.1. Overall survival

2.2.2. Distant disease-free survival

2.2.3. Breast cancer free interval (events are reappearance of invasive breast cancer at any site including contralateral disease)

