#### 6.1.2. Secondary end points:

- Overall survival (OS) is defined as the time from randomization to death from any cause.
- Distant disease-free survival (DDFS) is defined as the time from randomization to any recurrent or metastatic disease in distant sites (i.e., other than the local mastectomy scar/chest wall/skin, the ipsilateral breast in case of breast conservation,

or the ipsilateral axilla and internal mammary lymph nodes), second (non-breast) malignancy, or death from any cause, whichever occurs first.

- Breast cancer free interval (BCFI) is defined as the time from randomization to local (including recurrence restricted to the breast after breast conserving treatment), regional, or distant relapse, or contralateral breast cancer. In calculating BCFI, second (non breast) malignancies are ignored and deaths without cancer event are censored at the time of death as a competing event. Appearance of DCIS or LCIS either in the ipsilateral or in the contralateral breast is not considered a BCFI event, but should be recorded on the Follow-up Form (E).
- Sites of first DFS failure.
- Second (non-breast) malignancies
- Deaths without prior cancer event
- Adverse events

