## 9.2. Data analyses

The primary analysis will be undertaken with the intention-to-treat population of all randomized patients. The primary endpoint is disease-free survival (DFS: Section 6.1.1) and will be compared between treatment arms using a two-sided stratified logrank test with an overall experiment-wise alpha level equal to at most 0.05. Kaplan-Meier estimates of the DFS distributions will be calculated for each of the two treatment arms. Cox proportional hazards regression models will be used to investigate whether the treatment comparison is modified by adjustments for various covariates.

Other factors will be used to characterize the patients enrolled in the study and to provide descriptive statistics of outcomes according to subgroups of the population. These factors include age at randomization, body mass index, tumor size, tumor grade, number of positive lymph nodes, ER/PgR and HER2 status of the primary tumor, type of prior endocrine therapy, interval of time since the cessation of prior endocrine therapy. These analyses will be considered as secondary and descriptive.

The following secondary endpoints will be assessed: overall survival, distant disease-free survival, breast cancer-free interval, sites of first DFS failure, incidence of second (non-breast) malignancies, deaths without prior cancer event, incidence of targeted adverse events.

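### The SAP replaces the protocol's secondary endpoint DDFS with DRFI and plans no supportive DDFS analysis, so the protocol-defined composite would go unreported

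*SAP*

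**What the plan says.** **Protocol.** The summary lists DDFS among the secondary endpoints: "Secondary end points: overall survival (OS), distant disease-free survival (DDFS), breast cancer free interval (BCFI), sites of first failure". Section 2.2 repeats it: "2.2.2. Distant disease-free survival". Section 6.1.2 defines it as time from randomization to disease at a distant site (it lists the sites that are not distant, ending "or the ipsilateral axilla and internal mammary lymph nodes), second (non-breast) malignancy, or death from any cause, whichever occurs first"). Section 9.2 commits to analysing it: "The following secondary endpoints will be assessed: overall survival, distant disease-free survival, breast cancer-free interval".

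**SAP.** Section 2.3.2 announces the change: "Distant disease-free survival (DDFS) was a secondary endpoint in protocol. It will be replaced by a more modern definition". The new endpoint, DRFI, is the "duration of time from randomization to the first indication of invasive breast recurrence at a distant site". On patients without an event it says: "DRFI is censored at the date of last follow-up or date of death without distant recurrence".

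Sections 2.6.4 and 2.6.4.1 plan comparisons, tables and Kaplan-Meier plots for three secondary endpoints: BCFI, DRFI and OS. Second malignancies as site of first failure, and deaths without a prior cancer event, are summarised by arm. DDFS is not mentioned again.

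**The concern.** DRFI is a different endpoint, not a new name for DDFS. Of the three kinds of DDFS event, two (second non-breast malignancy and death without distant recurrence) stop being events. DDFS asks how long patients live free of distant disease, other cancers and death. DRFI asks only about distant spread of the breast cancer.

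The replacement is a reasonable endpoint. The difficulty is that the endpoint named in the protocol disappears from the planned outputs. A reader of the trial report who goes back to the protocol would find a secondary endpoint with no result and could not judge whether the two definitions agree. Reporting the protocol-defined endpoint beside its replacement is the usual guard against any question of selective reporting. It matters somewhat more here because SAP 1.5 already describes both interim efficacy analyses, so the text as it stands was written after them.

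**Working it through.** The plan gives no figure for DDFS or DRFI, so the check is mainly a comparison of definitions and outputs.

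**Step 1: how typical patients count** (protocol 6.1.2; SAP 2.3.2, 2.6.4 and 2.6.4.1)

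| Course of disease | DDFS | DRFI | Where else the SAP shows it |
|---|---|---|---|
| Distant breast recurrence first | Event | Event | BCFI, site of first failure |
| Death, no prior cancer event | Event | Censored at death | OS; deaths without prior cancer event |
| Local recurrence, then death without distant disease | Event at death | Censored at death | OS; BCFI for the local recurrence |
| Second malignancy first, alive, no distant disease | Event | No event | Second malignancies as first failure |
| Second malignancy first, later distant recurrence | Event at second malignancy | Event at the later recurrence | Second malignancies as first failure; BCFI |
| Local recurrence, later second malignancy, alive, no distant disease | Event at second malignancy | No event | BCFI for the local recurrence; second malignancy uncertain, see step 2 |

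Only the first row gives the same result under both definitions.

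**Step 2: can the other outputs stand in for DDFS?** In part. OS counts all deaths by arm, and second malignancies that are first events are tabulated by arm. For later second malignancies the SAP is unclear: 2.3.2 lists their incidence without restriction, while the outputs in 2.6.4 and 2.6.4.1 are limited to first failures. For coincident events, 2.3.2 says: "If second malignancy is coincident with breast cancer recurrence then site of first failure is considered as the breast cancer recurrence". Even complete component tables would not give the hazard ratio, confidence interval or 5-year estimate of the composite, because these need each patient's first qualifying date.

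**Step 3: timing.** SAP 1.5 reports the interim analyses at 324 and 454 DFS events, the second for the spring 2015 monitoring report. SAP 2.4 plans the data cut-off before November 1, 2016. The text therefore postdates both interim analyses and precedes the planned cut-off. It does not date the decision to change.

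**Step 4: size.** The documents give no counts of distant recurrences, second malignancies or deaths, so the difference between DDFS and DRFI cannot be derived. The nearest figure is the allowance in protocol 9.3, which concerns DFS. Four-year DFS of 91.8% in node-positive patients, counting breast events only, is lowered to an assumed 90% because deaths and second malignancies are added.

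- Risk scale: (0.918 − 0.900) / (1 − 0.900) = 0.018 / 0.100 = 18%.
- Hazard scale: −ln 0.900 = 0.1054; −ln 0.918 = 0.0856; (0.1054 − 0.0856) / 0.1054 = 0.0198 / 0.1054 = 18.8%.

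The design thus attributes roughly 18 to 19% of four-year DFS events to the kinds of event that DRFI drops. This is a planning assumption for another endpoint. It suggests only that these events were not expected to be negligible.

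**Step 5: which sites are distant.** The list of non-distant sites in protocol 6.1.2 omits ipsilateral supraclavicular nodes and the contralateral breast. Section 6.2.2 classes those nodes as regional, 6.2.3 treats contralateral breast failure as its own category, and 6.2.4 makes distant whatever remains. Read literally, 6.1.2 would make both sites distant for DDFS. A restored DDFS analysis needs this conflict settled.

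**The case against.** The strongest reply is that little is lost. The SAP states the change openly and before the planned cut-off. The protocol promises only that DDFS will be assessed and specifies no method for it. DDFS shares second malignancy and death with the primary endpoint, so a breast-cancer-specific interval may be more informative. No alpha is assigned to secondary endpoints. All of this stands, and it limits the weight of the point. It does not explain why the protocol-defined analysis should go unreported when its data are in hand.

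Four stronger readings are tempting, and the documents do not support them.

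- *The change was prompted by results.* Protocol 9.5 restricts efficacy analyses by arm to the formal interim time points, and nothing says when or by whom the change was decided. A fuller reason or a date may stand in SAP front matter that is not in the available text, so the brevity of the stated reason is not counted as a defect.
- *Deaths after a cancer event drop out of view.* They do not: OS counts every death, by arm.
- *Later second malignancies appear nowhere.* The SAP is ambiguous on this (step 2). Protocol 6.3.1 and 7.3 also require second malignancies to be reported on the Follow-up Form and as serious adverse events, whenever they are diagnosed.
- *DRFI is itself undefined for supraclavicular recurrence.* The faulty list belongs to the DDFS definition. For DRFI, protocol 6.2.2 and 6.2.4 already class ipsilateral supraclavicular nodes as regional.

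**Conclusion.** The point holds in limited form. A secondary endpoint that the protocol says will be assessed is replaced by a narrower one, and the SAP plans no analysis of the endpoint as the protocol defines it. If the SAP is followed, the DDFS hazard ratio, confidence interval and 5-year estimate will not be reported.

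The effect is confined to one secondary endpoint and its numerical size is unknown. The primary DFS test and its target of 647 events are untouched. The conclusion rests on the visible SAP text and assumes that no DDFS analysis is specified elsewhere. It implies nothing about the motive for the change.

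**What to change.** Keep DRFI and label it as introduced in the SAP. Add DDFS, with the protocol's event components, to SAP 2.6.4 and 2.6.4.1 as a supportive secondary analysis: stratified hazard ratio, 95% confidence interval, 5-year estimate and Kaplan-Meier plot, as for the other secondary endpoints.

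For that analysis, reconcile the non-distant site list in protocol 6.1.2 with the classification in 6.2.2 to 6.2.4, state the result in the SAP, and use the same classification for DRFI.

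The cost is one table row, one plot and one line of definition. Recurrence sites, second malignancies and deaths are already recorded on the Follow-up Form (protocol 6.2, 6.3.1 and 6.3.2), so no new data are needed.

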## 6.2. Diagnosis of Events

The diagnosis of failure event depends on evidence of recurrent disease which can be classified as either suspicious or acceptable. In either case, this should be specified and reported. Acceptable evidence of failure according to site is defined below. Any events not included in this section are considered unacceptable as evidence of recurrent disease. Failures include: local, regional, contralateral breast, and distant failures, second (non-breast) primaries, and deaths without recurrence. Histological confirmation of cytological evidence of recurrence is recommended in easily accessible lesions.

The date of failure event is the time of first appearance of a suspicious lesion, later proven to be a definitive recurrence or metastasis. All events described below should be recorded on the Follow-up Form (E).

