#### 6.3.2. Death without prior cancer event

Any death without a prior cancer event described in 6.2.1 through 6.2.4 above is considered a DFS event. The death, date, and the cause should be reported on the Follow-up Form (E) regardless of whether it occurs during or after trial treatment, and on the Serious Adverse Event Forms (SAE-A and SAE-B) if occurring during trial treatment.

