2.6.4.1 Tables and Figures

Tables:

- Primary treatment comparison for each of the 3 secondary endpoints: N events and patients, HR, 95% CI, log-rank test statistic and p-value, 5yr DFS, SE and 95% CI
- Sites of first failure, overall and by treatment group
- Types of second non-breast malignancies, as site of first failure, overall and by treatment group.
- Death without recurrence (list of patients with cause of death)

Figures:

- KM plots of BCFI, by treatment group, for entire analysis population (*y-axis: Percent Free from Breast Cancer; x-axis: Time since Randomization (12-month intervals); x-axis limited to 6 years (median survival plus 1 year) and numbers at risk at each 12-monthly interval*)
- KM plots of DRFI, by treatment group, for entire analysis population (*y-axis: Percent Free from Distant Recurrence; x-axis: Time since Randomization (12-month intervals); x-axis limited to 6 years (median survival plus 1 year) and numbers at risk at each 12-monthly interval*)
- KM plot of OS, by treatment group, for entire analysis population (*y-axis: Percent Alive; x-axis: Time since Randomization (12-month intervals); x-axis limited to 6 years (median survival plus 1 year) and numbers at risk at each 12-monthly interval*)

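### DRFI and BCFI are censored at death whatever the cause, so a breast cancer death without the required documented recurrence is a non-event

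*SAP*

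**What the plan says.** SAP 2.3.2 drops the protocol's distant disease-free survival (DDFS) and puts DRFI in its place, defined as "the duration of time from randomization to the first indication of invasive breast recurrence at a distant site". Its censoring rule is: "In the absence of an event, DRFI is censored at the date of last follow-up or date of death without distant recurrence". For BCFI the SAP says: "In the absence of an event, BCFI is censored at the date of last follow-up or date of death without prior breast cancer event". Protocol 6.1.2 has the same rule for BCFI: "deaths without cancer event are censored at the time of death as a competing event". None of these definitions refers to cause of death.

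The DDFS that DRFI replaces did count these women. Its event list in protocol 6.1.2 ended with "second (non-breast) malignancy, or death from any cause, whichever occurs first".

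Protocol 6.2 sets out what evidence of recurrence is acceptable at each site and adds: "Any events not included in this section are considered unacceptable as evidence of recurrent disease". Cause of death is not on the list. Protocol 6.3.2 defines a prior cancer event by reference to 6.2.1 to 6.2.4.

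Cause of death is collected. Protocol 6.3.2 says: "The death, date, and the cause should be reported on the Follow-up Form (E)". The SAP's one stated use of it is a listing in 2.6.4.1: "Death without recurrence (list of patients with cause of death)".

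**The concern.** Every patient is disease-free at entry, so a later death from breast cancer means that the disease came back. For an endpoint meant to measure the return of breast cancer, such a death is the outcome of interest. It is not a competing cause that removes the patient from risk. Censoring it assumes that she would otherwise have had the same future risk as women still under observation, which cannot be right. The censoring is informative.

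BCFI and DRFI are the two time-to-event endpoints specific to breast cancer. SAP 2.6.4 and 2.6.4.1 report both with hazard ratios, log-rank p-values and Kaplan-Meier plots. As written, both can miss fatal breast cancer: their event counts would be too low and their event-free percentages too high.

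**Working it through.** **The plan's own figure.** The documents give a design figure for DFS only.

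- Effect: 0.90^0.80 = 0.91917, which matches the stated 91.917%.
- Fixed design: 4 × (1.960 + 0.842)² / (ln 0.80)² gives 631 events.
- With the planned looks at 40%, 70% and 100% information, the required drift under Lan-DeMets O'Brien-Fleming spending is 2.8372, and 4 × 2.8372² / (ln 0.80)² = 646.7, or 647. Classical O'Brien-Fleming boundaries give 643.0.

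So 647 is reproduced, and this point does not touch it.

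**How each endpoint treats a woman who dies of breast cancer.** This follows from SAP 2.3.1 and 2.3.2 with protocol 6.1 to 6.3.

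| Documented before death | DFS | BCFI | DRFI | OS |
|---|---|---|---|---|
| Nothing meeting 6.2 | event at death | censored at death | censored at death | event |
| Only a local, regional or contralateral invasive event | event at that failure | event at that failure | censored at death | event |
| Distant recurrence | event | event | event | event |

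The first row can arise under the protocol. An enlarged liver with abnormal liver tests (6.2.4.5), or a new pleural effusion without positive cytology or histology (6.2.4.3), is suspicious only. If the patient dies before further work-up, nothing acceptable is recorded.

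**Size.** The documents give no number of DRFI or BCFI events and no number of breast cancer deaths without the required documentation. The figures below are therefore illustrations. Assume that a share *f* of true DRFI events is censored in this way, equal in both arms and constant over time. Reported DRFI is then S^(1−f), where S is the true value. Assume also 300 true events. Approximate power at a hazard ratio of 0.80 with *e* counted events is Φ(√e × |ln 0.80| / 2 − 1.96).

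| f | Events counted | Reported 5-year DRFI if true value is 93% | Overstatement (points) | Power |
|---|---|---|---|---|
| 0 | 300 | 93.00% | 0 | 48.9% |
| 1% | 297 | 93.07% | 0.07 | 48.5% |
| 2% | 294 | 93.14% | 0.14 | 48.1% |
| 5% | 285 | 93.34% | 0.34 | 47.0% |
| 10% | 270 | 93.68% | 0.68 | 45.0% |

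For the same range of *f*, the overstatement is 0.09 to 0.95 points if true DRFI is 90%, and 0.05 to 0.49 points if it is 95%.

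**Hazard ratio (B versus A).** If the shares differ by arm, the hazard ratio is multiplied by about (1 − f_B)/(1 − f_A). With f_A = 2% and f_B = 5% this is 0.95/0.98 = 0.969; with the shares reversed it is 0.98/0.95 = 1.032. With equal shares it is 1.

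**The case against.** The best case against acting is that few patients would be affected. Protocol 6.2 accepts imaging as well as histology at most distant sites: CT or MRI for lung, liver and nodes, several modalities for bone, and CT or MRI with a suspicious clinical picture for the central nervous system. Suspicious findings must also be reported, a medical reviewer looks at each case (protocol 11.5), and a recurrence once proven is dated back to first suspicion. The SAP speaks of a first indication and refers to a group standard not given in full, so cases may in practice be coded more sensibly than the text requires. All this bears on frequency and stands. It does not supply a rule for the deaths that remain, and no other section counts a breast cancer death as a recurrence.

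It can also be said that these deaths are already visible, because SAP 2.6.4 summarises deaths without a prior cancer event by treatment group and 2.6.4.1 lists their causes. That covers the first row of the case table. It misses women with an earlier local, regional or contralateral event, who do not belong in that listing, and it leaves the hazard ratios and curves unchanged.

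A reader might infer three stronger points that the documents do not support:

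- *That DFS contradicts these endpoints.* A documented chest-wall failure is already both the DFS and the BCFI event. With no documented event, DFS counts the death because it is a composite that counts any death.
- *That the problem grows sharply after month 60.* Before month 60 the mandatory follow-up assessments in protocol 7.1 are also only physical examination and adverse events, with most imaging done if medically indicated. What changes is mainly visit frequency and the yearly mammogram, and legend G still recommends the latter at yearly intervals. The SAP plots stop at 6 years, described as median follow-up plus 1 year, so median follow-up is expected to be about 5 years.
- *That a number of lost events can be stated.* This needs the share of breast events that become distant and the share known only from a death. The documents give neither.

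**Conclusion.** The point holds as a gap in two secondary endpoint definitions. Read literally, SAP 2.3.2 treats some fatal breast cancer as non-informative censoring. Both DRFI and BCFI are affected when no acceptable evidence was recorded, and DRFI alone when only a local, regional or contralateral event was documented. The patient is a non-event up to her death and contributes no event-free time after it.

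The frequency is unknown and may be near zero. Under the assumptions shown (1–10% of true DRFI events affected, true 5-year DRFI of 93%), the overstatement is about 0.07 to 0.68 points. A reader might infer a biased treatment comparison. That needs the share to differ between arms, and nothing in the documents suggests that it does. Primary DFS, the 647 events and OS stand as they are. The change is still worth making, because it is cheap and affects which events enter two endpoints reported with hazard ratios and p-values.

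**What to change.** In SAP 2.3.2, before database lock:

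- **DRFI:** count a death attributed to breast cancer on Form E, with no earlier documented distant recurrence, as an event at date of death.
- **BCFI:** do the same where no breast cancer event was documented earlier.
- **Both:** censor at death only for other causes, report by arm the number of deaths reclassified in this way, and give the present definition as a sensitivity analysis.

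The cost is a few lines of SAP text and one extra run per endpoint; cause of death is already collected. The small downside is reliance on site-reported cause of death, which can add false events, and the documents describe no blinding. Dating such an event at death also departs from the rule that uses the date of first suspicion. The sensitivity analysis shows whether either matters. The revised BCFI would differ from protocol 6.1.2, so the SAP should record the change, as it already does for the replacement of DDFS.
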